#### **6.2.2. Primary Safety Endpoint and Safety Considerations**

Primary safety endpoint: The overall incidence and severity of all adverse events including clinically significant thrombocytopenic events using Common Toxicity Criteria v 4.0.

An adverse event is any untoward medical occurrence that may present during treatment with a pharmaceutical product but which does not necessarily have a causal relationship with this treatment. Adverse events (AEs) will be collected using the Leukemia AE guidelines.

Adverse drug reaction is a response to a drug which is noxious and unintended and which occurs at doses normally used in man for prophylaxis, diagnosis, or therapy of disease or for the modification of physiologic function.

All “suspected adverse reactions” (as defined in 21 CFR 312.32(a)) will be captured in the case report forms. For abnormal chemical values grade 3 or 4, the apogee will be reported per course in the CRF.

Assessing causal connections between agents and disease is fundamental to the understanding of adverse drug reactions. In general, a drug may be considered a contributory cause of an adverse event if, had the drug not been administered, 1) the event would not have happened at all, 2) the event would have occurred later than it actually did, or 3) the event would have been less severe.

The Investigator or physician designee is responsible for verifying and providing source documentation for all adverse events and assigning the attribution for each event for all subjects enrolled on the trial. Protocol specific data and adverse events will be entered into PDMS/CORE, the electronic case report form for this protocol.

#### **6.2.2.1. Serious Adverse Event Reporting (SAE)**

An adverse event or suspected adverse reaction is considered “serious” if, in the view of either the investigator or the sponsor, it results in any of the following outcomes:

- Death
- A life-threatening adverse drug experience – any adverse experience that places the patient, in the view of the initial reporter, at immediate risk of death from the adverse experience as it occurred. It does not include an adverse experience that, had it occurred in a more severe form, might have caused death.
- Inpatient hospitalization or prolongation of existing hospitalization
- A persistent or significant incapacity or substantial disruption of the ability to conduct normal life functions.
- A congenital anomaly/birth defect

Important medical events that may not result in death, be life-threatening, or require hospitalization may be considered a serious adverse drug experience when, based upon appropriate medical judgment, they may jeopardize the patient or subject and may require medical or surgical intervention to prevent one of the outcomes listed in this definition. Examples of such medical events include allergic bronchospasm requiring intensive treatment in an emergency room or at home, blood dyscrasias or convulsions that do not result in inpatient hospitalization, or the development of drug dependency or drug abuse (21 CFR 312.32).

- Important medical events as defined above may also be considered serious adverse events. Any important medical event can and should be reported as an SAE if deemed appropriate by the Principal Investigator or the IND Sponsor, IND office.

All events occurring during the conduct of a protocol and meeting the definition of a SAE must be reported to the IRB in accordance with the timeframes and procedures outlined in “The University of Texas M. D. Anderson Cancer Center Institutional Review Board Policy for Investigators on Reporting Unanticipated Adverse Events for Drugs and Devices”. Unless stated otherwise in the protocol, all SAEs, expected or unexpected, must be reported to the IND Office, regardless of attribution (within 5 working days of knowledge of the event).

Only unexpected AEs will be recorded in the Case Report Form (CRF). The Principal Investigator will sign and date the PDMS or CORE Case Report Form toxicity pages per each patient at the completion of each course. Following signature, the Case Report Form will be used as source documentation for the adverse events for attribution.

**All life-threatening or fatal events**, that are unexpected, and related to the study drug, must have a written report submitted within **24 hours** (next working day) of knowledge of the event to the Safety Project Manager in the IND Office.

**Unless otherwise noted, the electronic SAE application (eSAE) will be utilized for safety reporting to the IND Office and MDACC IRB. MDACC.**

**Serious adverse events will be captured from the time of the first protocol-specific intervention, until 30 days after the last dose of drug unless the participant withdraws consent. Serious adverse events must be followed until clinical recovery is complete and laboratory tests have returned to baseline, progression of the event has stabilized, or there has been acceptable resolution of the event.**

**Additionally, any serious adverse events that occur after the 30 day time period that are related to the study treatment must be reported to the IND Office. This may include the development of a secondary malignancy.**

The following SAEs are not subject to expedited reporting, but would still be included in the annual report via the SAE log.

- a. Infection or cytopenias leading to hospitalization or prolongation of hospitalization  
Disease progression leading to death, life-threatening AE, hospitalization or prolongation of hospitalization, or disability.

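### Section 6.2.2.1 keeps expected adverse events out of the case report form that Section 6.2.2 requires them to be entered in; following 6.2.2.1 biases reported adverse event incidence downward

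*Combined protocol and SAP*

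**What the plan says.** Two current sections give rules for the same form.

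- **Section 6.2.2** defines the primary safety endpoint as "The overall incidence and severity of all adverse events including clinically significant thrombocytopenic events". Suspected adverse reactions, all of them, "as defined in 21 CFR 312.32(a)) will be captured in the case report forms". It adds: "Protocol specific data and adverse events will be entered into PDMS/CORE, the electronic case report form for this protocol". Grade 3 or 4 chemistry values have a rule of their own: "For abnormal chemical values grade 3 or 4, the apogee will be reported per course in the CRF". None of these sentences distinguishes expected from unexpected events. The section also says: "Adverse events (AEs) will be collected using the Leukemia AE guidelines". Those guidelines are not reproduced in the document.
- **Section 6.2.2.1** says: "Only unexpected AEs will be recorded in the Case Report Form (CRF". The principal investigator then signs the PDMS or CORE toxicity pages at the end of each course, after which "the Case Report Form will be used as source documentation for the adverse events for attribution".

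The results that depend on these records are the primary safety endpoint in 6.2.2, the treatment-related adverse event objective and endpoint in 1.2 and 6.2.3, and the summary of recorded treatment-emergent events in 8.4.

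**The concern.** The two rules cannot both be followed. Section 6.2.2 requires an expected, drug-related event in the CRF, and 6.2.2.1 excludes it. The restrictive rule also conflicts with an endpoint defined on all adverse events.

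The documents do not define expected. In ordinary use it covers the known effects of the study drugs. Section 2.1 describes severe thrombocytopenia as common under decitabine, and Section 2.2 lists liver enzyme elevation among the known effects of eltrombopag. If such effects count as expected, 6.2.2.1 removes from the CRF a kind of event that the primary safety endpoint names.

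This is a single-arm trial of a combination, so its adverse event rates will be read as absolute figures. No control arm under-records to the same degree. If staff differ in which rule they follow, the rates also depend on who did the recording.

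**Working it through.** The plan gives no figure on this point, so the check compares the texts and then works out the direction and unit of the bias.

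**Step 1: is it the same form?** Yes. Section 6.2.2 calls PDMS/CORE the electronic case report form, and 6.2.2.1 refers to the PDMS or CORE Case Report Form.

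**Step 2: what does each rule do with each class of event?**

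| Class of event | 6.2.2 | 6.2.2.1 | Other route named |
|---|---|---|---|
| Unexpected | in CRF | in CRF | not needed |
| Expected, serious | in CRF | not in CRF | IND Office, eSAE, SAE log, study supporter |
| Expected, non-serious, drug-related | in CRF | not in CRF | none, except peak grade 3–4 chemistry values |
| Expected, non-serious, not drug-related | in CRF, subject to the unseen guidelines | not in CRF | none, except peak grade 3–4 chemistry values |

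The rules agree only in the first row. The gap with no other route is the expected, non-serious events in the last two rows, apart from the chemistry values.

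**Step 3: is the problem ascertainment or entry?** It is entry. Sections 4.1 and 5.2 have adverse events assessed at every visit, and 6.2.2 makes the investigator "responsible for verifying and providing source documentation for all adverse events and assigning the attribution for each event". The information should exist in source records. What fails under 6.2.2.1 is its transfer to the dataset.

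**Step 4: direction and unit.** For one event type, let X be the number of treated patients with at least one such event. Let m be the number of those whose events of that type are all left out of the CRF. N is the safety set, meaning everyone who received at least one dose (Section 6.3.3). At full accrual N = 40 (Sections 4.1 and 8).

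- True incidence = X/N
- Reported incidence = (X − m)/N
- Difference = m/N, with m ≥ 0

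Reported incidence therefore equals or falls below true incidence, and never exceeds it. The loss per omitted patient is 1/40 = 0.025, or 2.5 percentage points. The documents do not give m. As a scale only: m = 1 gives 2.5 points, m = 4 gives 4/40 = 10 points, and m = 8 gives 8/40 = 20 points.

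**Step 5: does the toxicity stopping rule depend on this?** Possibly. Section 8 counts grade 3–4 clinically relevant non-hematologic toxicity and drug-related serious events, with no limit by expectedness, but it does not say which records the quarterly review uses. An effect is not established, and the conclusion does not rest on one.

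**The case against.** The strongest reply accepts the clash in wording and disputes its consequence.

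- **Data source.** Section 8.4 speaks of recorded events without naming the CRF, so the under-count is inferred. This stands as a caution. But PDMS/CORE is the only place the protocol names for adverse event data apart from the serious-event systems, and no plan exists to retrieve the rest from source records.
- **The Leukemia AE guidelines.** They govern collection and might limit entry or settle the matter. Their content cannot be checked here. Section 6.2.2.1 does not refer to them, however, and 6.2.2 does not say that they restrict the CRF to unexpected events.
- **Other data.** Blood counts and chemistries are summarized at each time point (Section 8.3), and platelet transfusions go on the CRF (Section 4.7.4), so cytopenias and liver abnormalities would remain visible. That is true, but these are not graded and attributed adverse event records and do not fill the 8.4 tables.
- **Sign-off.** The investigator's review at the end of each course is a check on what was entered. It does not restore events that the rule keeps out.
- **Placement.** The sentence sits under serious-event reporting and may be meant for serious events only. It says AEs, and the next sentence covers toxicity pages for every patient. Even on the narrow reading it would bar expected serious reactions that 6.2.2 wants in the form.
- **Size.** The loss is unknown, and 2.5 points per patient would hold in any trial of 40. This stands: the figure is a unit and does not estimate the bias.

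**Conclusion.** The contradiction is certain on the text. Under 6.2.2.1 the CRF cannot deliver the all-event primary safety endpoint, the treatment-related endpoint or the 8.4 tables; under 6.2.2 it can. Recorded incidence for an event type can only equal or fall below the truth, and it falls whenever a patient's only events of that type are expected ones left out.

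The under-count rests on two assumptions: that the safety tables are built from PDMS/CORE, and that the unseen guidelines do not override 6.2.2.1. The primary efficacy endpoint and the separate reporting of serious events are unaffected. The point should be corrected because the primary safety result turns on which of two sentences the staff follow.

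**What to change.** Replace the sentence in 6.2.2.1 with, for example: *Adverse events are recorded in the CRF regardless of expectedness, with CTCAE v4.0 grade, dates and attribution.*

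Before doing so, check the Leukemia AE guidelines. If they limit what is entered, state the limit in the protocol, word the 6.2.2 endpoint and the 8.4 tables to match, and make sure that every event counted under the Section 8 toxicity definition is still recorded.

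A sentence in Section 8 saying that the quarterly toxicity counts draw on both the CRF and the SAE log would also help, but is optional for this point.

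The cost is one replaced sentence, the optional addition, and matching wording in 6.2.2 and 8.4 if the guidelines require it. There is some extra data entry at visits where adverse events are already assessed. No dose, schedule or clinical rule changes.

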## 8.4. Safety Endpoints

The incidence of adverse events will be summarized by system organ class and by preferred term according to the MedDRA dictionary for each treatment group. This summary includes all treatment-emergent adverse events recorded from the start of investigational product on this study, or any worsening of adverse events initially experienced before initiation of this study.

Narratives of “on-study” deaths, serious and significant adverse events, including early withdrawals due to adverse events, may also be provided.

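### Section 6.2.2.1 keeps expected adverse events out of the CRF, which contradicts the all-AE safety endpoint in 6.2.2 and would leave known clinical toxicities under-reported in the 8.4 summary

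*Combined protocol and SAP*

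**What the plan says.** Section 6.2.2 defines the endpoint without regard to expectedness: "Primary safety endpoint: The overall incidence and severity of all adverse events including clinically significant thrombocytopenic events using Common Toxicity Criteria v 4.0". It then gives four collection rules.

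- The general standard: "Adverse events (AEs) will be collected using the Leukemia AE guidelines". Those guidelines are not part of the text available here.
- All suspected adverse reactions, "as defined in 21 CFR 312.32(a)) will be captured in the case report forms".
- Laboratory peaks: "For abnormal chemical values grade 3 or 4, the apogee will be reported per course in the CRF".
- The investigator verifies, documents and attributes every adverse event, and adverse events are entered in PDMS/CORE, which 6.2.2 names as the electronic CRF.

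Section 6.2.2.1 then says "Only unexpected AEs will be recorded in the Case Report Form (CRF". It goes on to have the principal investigator sign the CRF toxicity pages after each course, and adds that after signature "the Case Report Form will be used as source documentation for the adverse events for attribution". Serious events have a separate route: "all SAEs, expected or unexpected, must be reported to the IND Office, regardless of attribution".

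Downstream, objective 1.2 assesses safety by all treatment-related adverse events. Section 8.4 reports on what was captured: "This summary includes all treatment-emergent adverse events recorded from the start of investigational product on this study". The toxicity rule in Section 8 counts clinically relevant non-hematologic events of grade 3 or 4 and drug-related SAEs. It makes no distinction by expectedness and names no data source for the quarterly review.

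**The concern.** Expectedness normally decides how fast an event is reported. Here one sentence makes it decide whether the event is recorded at all. The toxicities already known for the two drugs are the ones a reader most wants counted in a combination study, and that sentence would remove them.

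The 8.4 summary would be affected directly, because it can show only what was recorded. A low or empty row for a known clinical toxicity could mean that it did not occur or that it was never entered, and the table would not tell the reader which. The toxicity rule could also be affected if it is run from the same CRF. The response-rate endpoint, the futility rule and the sample size are not involved.

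**Working it through.** **1. Which events depend on the conflicting sentence.** Each class of event, with its route if 6.2.2.1 is followed literally:

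| Class of event | Route | Lost? |
|---|---|---|
| SAE, expected or not | IND Office through the electronic SAE system (6.2.2.1); also the drug supplier (6.2.2.3) | No |
| Grade 3-4 abnormal chemistry | Peak per course in the CRF (6.2.2) | No |
| Liver events meeting 4.8.4 | Reported to the drug supplier within 24 hours | No |
| Other chemistry and blood counts, including platelets | Collected under 5.2, summarised under 8.3 | Values kept |
| Unexpected, non-serious AE | CRF (6.2.2.1) | No |
| Expected, non-serious, non-laboratory AE | CRF under 6.2.2; excluded by 6.2.2.1 | Yes |

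Only the last row turns on which sentence is obeyed. Liver enzyme elevation and thrombocytopenia are expected, but they fall in the laboratory rows and are not examples of the gap.

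**2. What the 8.4 table would show.** Cataract is a known clinical risk in 2.3.4 and serves as an illustration. That section gives 4% (ITP extension), 7% (controlled ITP trials, the same as placebo) and 8% (hepatitis C trials, placebo 5%). Assume that one of these rates applies to the 40 patients. The expected number is 40r, and with full recording the chance of seeing none is (1 - r)^40.

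- r = 0.04: 1.6 patients expected; 0.96^40 = 0.195
- r = 0.07: 2.8 expected; 0.93^40 = 0.055
- r = 0.08: 3.2 expected; 0.92^40 = 0.036

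If expected cases are not entered, the table shows 0/40. The exact 95% upper limit is then 1 - 0.025^(1/40) = 8.8%. The direction is clear, but the size is not established. The rates come from other populations, 5.2 schedules no eye examination, and at 4% an empty row would occur about one time in five even with perfect recording.

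**3. The plan's toxicity figures.** With prior beta(0.6, 1.4) and x toxicities in n patients, the posterior is beta(0.6 + x, 1.4 + n - x). The rule stops when Pr(p > 0.30) exceeds 0.90. At n = 5 this probability is 0.875 for x = 3 and 0.975 for x = 4, so the boundary is 4. At n = 20 it is 0.807 for x = 8 and 0.906 for x = 9, so the boundary is 9. Repeating this at all seven looks gives 4, 6, 8, 9, 11, 13 and 15, as in Table 3.

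An exact binomial recursion through these looks, in cohorts of 5 up to 40 patients, gives:

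| True rate | P(stop), recomputed | P(stop), Table 4 | Average n, recomputed | Average n, Table 4 |
|---|---|---|---|---|
| 0.10 | 0.0006 | 0.0006 | 40.0 | 40.0 |
| 0.20 | 0.021 | 0.020 | 39.4 | 39.4 |
| 0.30 | 0.186 | 0.186 | 35.8 | 35.8 |
| 0.40 | 0.583 | 0.583 | 26.8 | 26.8 |
| 0.50 | 0.905 | 0.905 | 17.3 | 17.3 |

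The printed design is right. It assumes that every qualifying toxicity is counted.

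**4. Sensitivity of the rule, under an assumption.** Let u be the share of patients with a qualifying toxicity for whom nothing qualifying reaches the review. The documents give no value for u, and zero is compatible with them. The rate seen by the rule is (true rate) x (1 - u).

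| u | True 0.40: rate seen, P(stop) | True 0.50: rate seen, P(stop) |
|---|---|---|
| 0 | 0.40, 0.583 | 0.50, 0.905 |
| 10% | 0.36, 0.409 | 0.45, 0.775 |
| 25% | 0.30, 0.186 | 0.375, 0.474 |
| 50% | 0.20, 0.021 | 0.25, 0.073 |

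This shows how the rule responds to missed events. It does not estimate what would happen in this trial.

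**The case against.** The best defence is that 6.2.2, the governing section, already orders full collection. It does so through the suspected-reaction rule, PDMS/CORE entry, and the investigator's duty to document and attribute every event. On that view the harm requires staff to follow one sentence placed under SAE reporting. The placement does not settle the matter. The sentence speaks of AEs in general, the next one concerns toxicity pages signed each course, and SAEs have their own route. The Leukemia AE guidelines may resolve the conflict, but they cannot be checked here, and nothing in 6.2.2.1 points to them.

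Two further parts of the defence stand and limit the point.

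- A reader might infer that unrecorded events are lost for good. The documents do not support that. Section 7.5 lists hospital records and clinical charts as source documents, 4.3 obtains records from local physicians, and 4.5.1 requires visits to the trial centre at least every 3 months. Partial recovery is possible.
- A reader might infer that the stopping rule is disabled, or that the fall in P(stop) in step 4 is a finding. It is neither. A missed event would have to be grade 3-4, non-hematologic, clinically relevant, expected, non-serious and non-laboratory. Section 8 refers to toxicity data, not CRF data. One of the two reviewers is the principal investigator, who signs the toxicity pages, and 4.8.1 has treatment held for clinically significant grade 3-4 non-hematologic toxicity.

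Nor would the endpoint shrink to unexpected events alone, since serious and laboratory events still arrive.

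**Conclusion.** The contradiction is real, and 6.2.2.1 is wrong as written. If followed, it leaves expected, non-serious, non-laboratory adverse events out of the CRF. The 8.4 summary then understates known clinical toxicities and meets neither the 6.2.2 endpoint nor the treatment-related objective in 1.2. This rests on two assumptions: that sites would obey the 6.2.2.1 sentence over 6.2.2, and that known clinical risks such as those in 2.3 would be classed as expected.

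The number of events affected cannot be derived from the documents. Any effect on the toxicity rule further requires that the quarterly review use the CRF alone, and its size is likewise unknown. This is a conflict in the data-collection wording and not a numerical error. It should be corrected because the safety table depends on it and the correction is small.

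**What to change.** Replace the 6.2.2.1 sentence with:

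> Adverse events, expected or unexpected, will be recorded in the CRF as set out in 6.2.2, with CTCAE v4.0 grade and attribution; expectedness determines expedited reporting only.

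Add to the toxicity monitoring text in Section 8:

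> The toxicity rule counts qualifying events, whether expected or unexpected, from the CRF and the SAE database.

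If reduced recording is intended, limit it by grade and not by expectedness, and restate 6.2.2 and 8.4 to match. If the Leukemia AE guidelines already settle what is recorded, 6.2.2.1 should refer to them. The same edit is a chance to align 1.2, which covers treatment-related events, with 6.2.2, which covers all events.

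The cost is somewhat more CRF entry. Section 5.2 already schedules adverse event assessment at every visit, so no visits or tests are added, and Tables 3 and 4 stay as they are. If patients are already enrolled, their charts need one review for expected events that were not entered.

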#### **Reporting to FDA:**

- Serious adverse events will be forwarded to FDA by the IND Sponsor (Safety Project Manager IND Office) according to 21 CFR 312.32
- **It is the responsibility of the PI and the research team to ensure serious adverse events are reported according to the Code of Federal Regulations, Good Clinical Practices, the protocol guidelines, the sponsor's guidelines, and Institutional Review Board policy.**

